9.2.4. Outcome of Adverse Events

Record the outcome of AEs as follows:

- Resolved
- Not resolved
- Fatal

9.2.5. Follow-up of Adverse Events

Any ongoing AEs should be followed until the earliest occurrence of one of the following:

- The AE has resolved or stabilized
- Completion of safety follow-up visit
- Start of new antitumor therapy
- Withdrawal of consent

- Death
- Other (eg, transfer to another hospital)

9.3. Laboratory Assessments

9.3.1. Reporting and Evaluation of Laboratory Test Results

All laboratory results must be reviewed by the Investigator. A new laboratory or instrumental abnormality that has a clinical impact on a patient (including eg, resulting in study drug dose reduction, treatment delay, treatment discontinuation or requirement of intervention) is considered an AE, unless it is considered part of clinical manifestations to a clinical diagnosis that is already reported as an AE.

All laboratory values that are out of the normal range are to be evaluated for their clinical impact before exposing the patient to the next dose of futibatinib.

The NCI-CTCAE Version 5.0 will be used to grade the severity of laboratory data.

9.3.2. Repeat Testing

Evaluation of any clinically significant laboratory test will be repeated, as clinically indicated, until the value returns to the baseline level or clinically stabilizes, or until another treatment is given.

9.4. Serious Adverse Events

9.4.1. Definitions of Serious Adverse Events

An SAE is any untoward medical occurrence that at any dose:

- Results in death
 - Death due to disease progression or relapse is not considered an SAE unless the investigator deems it possibly related to the study drug.
- Is life-threatening
 - The term "life-threatening" refers to an event in which the patient was at risk of death at the time of the event; it does not refer to an event which hypothetically might have caused death if it were more severe.
- Requires inpatient hospitalization or prolongation of existing hospitalization to treat the AE.
- The following are not considered hospitalizations for the purposes of assessing seriousness (however, one of the other serious criteria may apply):
 - Emergency room visits < 24 hours;
 - Hospitalizations for preplanned procedures;
 - Hospitalization for study-related treatment and procedures.

- Results in persistent or significant disability/incapacity, where disability is defined as a substantial disruption of a person's ability to conduct normal life functions, either reported or defined as per clinical judgment.
- Is a congenital anomaly/birth defect (if exposure to product just before conception or during pregnancy resulted in an adverse outcome in the child).
- Is any other important medical event that based upon appropriate medical judgement may jeopardize the patient or may require medical or surgical intervention to prevent one of the other outcomes listed in the definitions above. (eg, may not result in death, be life-threatening, or require hospitalization).

9.4.2. Reporting of Serious Adverse Events (within 24 hours)

All SAEs occurring from the time the ICF is signed through the Safety Follow-up Period (90 days after the last dose of study drug or discontinuation of the Safety Follow-up Period, whichever is earlier) must be reported to Sponsor's Pharmacovigilance group or its designee **within 24 hours** from the time the Investigator first becomes aware of the SAE.

Comprehensive information available at the time of initial reporting (including narrative description, medical history, and concomitant medications) needs to be provided with careful consideration regarding causality and serious criterion. The SAE reporting process and contact information are provided in supplement guidelines.

After the initial SAE notification to the Sponsor's Pharmacovigilance group or its designee, all follow-up SAE information will be submitted each time they become available (for example, clinical diagnosis, outcome, causality assessment, results of specific investigations) on a follow up SAE form. The Investigator also must submit further information if it is required by the Sponsor or the director of the study site or an institutional review board (IRB)/independent ethics committee (IEC). Every SAE should be followed until it has resolved, stabilized, or returned to baseline.

9.4.3. Reporting of Deaths (within 24 hours)

All deaths (except disease progression) occurring from the time the ICF is signed through the Safety Follow-up Period (90 days after the last dose of study drug or discontinuation, whichever is earlier) must be reported within 24 hours from the time the Investigator first becomes aware of the death. The primary cause of the death should be reported as the SAE term, if available, and entered on the death page of the eCRF.

9.5. Other Safety Information

9.5.1. Pregnancy

If a patient inadvertently becomes pregnant while in the study, the study treatment must be immediately discontinued. Pregnancy information in a female patient (or for the female partner of a male patient) should be reported **as soon as possible** from the time the Investigator first becomes aware of a pregnancy or its outcome. This should be performed by completing a Pregnancy Form and faxing or e-mailing it to Sponsor's Pharmacovigilance or designee.

New and/or corrected information regarding the pregnancy obtained after submitting the initial Pregnancy Form must be submitted using an updated Pregnancy Form to the Sponsor’s Pharmacovigilance or designee. Pregnancies must be followed to outcome by the Investigator, even after study completion.

If the outcome of the pregnancy is a stillbirth, congenital anomaly/birth defect, or a serious event in the mother, it should be reported as an SAE to the Sponsor’s Pharmacovigilance or designee. Live births will be followed up by the Investigator. Any information that may be associated with the study drug should be reported even after study completion.

9.5.2. Overdose

For this study, an overdose of futibatinib is defined as the accidental or intentional use of the drug in an amount higher than the dose being studied. An overdose of pembrolizumab will be defined as any dose of 1000 mg or ≥ 5 times the indicated dose. An overdose or incorrect administration of study treatment is not itself an AE, but it may result in an AE. An overdose that results in an AE should be reported via faxing or emailing to Sponsor’s Pharmacovigilance or designee within 24 hours from the time the Investigator first becomes aware of its occurrence.

No specific information is available on the treatment of overdose of pembrolizumab or futibatinib; there is no known antidote in the case of futibatinib overdose. In the event of overdose, the participant should be observed closely for signs of toxicity. Appropriate supportive treatment should be provided if clinically indicated.

9.5.3. Pembrolizumab Events of Clinical Interest

Selected non-serious and SAEs are also known as Events of Clinical Interest (ECI) for pembrolizumab, and must be reported to the Sponsor.

Events of clinical interest for this trial include:

1. an overdose of pembrolizumab, as defined in [Section 9.5.2](#), that is not associated with clinical symptoms or abnormal laboratory results.
2. an elevated AST or ALT lab value that is greater than or equal to 3X the ULN and an elevated total bilirubin lab value that is greater than or equal to 2X the ULN and, at the same time, an ALP lab value that is less than 2X the ULN, as determined by way of protocol-specified laboratory testing or unscheduled laboratory testing.*

*Note: These criteria are based upon available regulatory guidance documents. The purpose of the criteria is to specify a threshold of abnormal hepatic tests that may require an additional evaluation for an underlying etiology. The trial site guidance for assessment and follow up of these criteria can be made available. It may also be appropriate to conduct additional evaluation for an underlying etiology in the setting of abnormalities of liver blood tests including AST, ALT, bilirubin, and ALP that do not meet the criteria noted above. In these cases, the decision to proceed with additional evaluation will be made through consultation between the study Investigators and the Sponsor Medical Monitor. However, abnormalities of liver blood tests that do not meet the criteria noted above are not ECIs for this trial.

For dose modification and other guidelines related to events of interest for both pembrolizumab and futibatinib, please see [Section 5.3](#) of this protocol.

10. CCI EVALUATION

10.1. CCI Assessments

Patients will be enrolled based on local assessment of FGFR mutation status; however, tissue samples (if available from fresh biopsy [preferred] or archived tissue collected after termination of the last therapeutic regimen) will be archived for central retrospective confirmation.

On-study collection of tumor tissue and blood/plasma will be performed from patients who consent, according to the schedule in [Table 1](#).

CCI

11. STATISTICAL CONSIDERATIONS

The statistical analysis methods will be documented in detail in the SAP.

11.1. Estimation of Sample Size

Approximately 20 patients will be enrolled in Cohort A. Sample size considerations are based on differentiating a historical control ORR per RECIST 1.1 of 35% or less, with a target ORR per RECIST 1.1 of 65%. Assuming the true ORR per RECIST 1.1 is 65%, the cohort has an approximate 80% power to reject the null hypothesis that the true ORR per RECIST 1.1 is $\leq 35\%$, considering a 2-sided alpha of 10%. With a sample size of 20, observing at least 12 responders will have a 90% CI lower bound excluding 10% (ORR per RECIST 1.1 of 60% with 90% CI (39.4% - 78.3%)).

Approximately 20 patients will be enrolled in Cohort B. Sample size considerations are based on differentiating a historical control ORR per RECIST 1.1 of 25% or less, with a target ORR per RECIST 1.1 of 50%. Assuming the true ORR per RECIST 1.1 is 50%, the cohort has an approximate 80% power to reject the null hypothesis that the true ORR per RECIST 1.1 is $\leq 25\%$, considering a 2-sided alpha of 10%. With a sample size of 20, observing at least 9 responders will have a 90% CI lower bound excluding 10% (ORR per RECIST 1.1 of 45% with 90% CI (25.9% - 65.3%)).

11.2. Planned Interim Analyses

The first interim analysis of safety will be performed after the 6-patient safety lead-in period; a second interim analysis of safety will be performed after a total of 10 patients have been enrolled (including the initial 6 patients enrolled in the safety lead-in period).

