Study TAS-120-203 is an open-label, non-randomized, multicenter Phase 2 study evaluating the combination of futibatinib and pembrolizumab in patients with advanced or metastatic UC who are not candidates to receive a platinum-based treatment regimen.

A treatment cycle is defined as 21 days. All enrolled patients will receive the same treatment regimen:

- Futibatinib at an oral (PO) dose of 20 mg daily (QD); and
- Pembrolizumab at an I.V. dose of 200 mg every 3 weeks (Q3W).

Treatment will continue until disease progression, unacceptable toxicity, or any other of the criteria for treatment discontinuation is met; of note, pembrolizumab may be administered for a maximum of 35 doses or a maximum duration of 2 years, whichever is earlier.

The study will begin with a safety lead-in period. During this period, a total of 6 patients with advanced or metastatic UC will be enrolled and treated for at least one 21-day cycle. Patients will be enrolled into this initial safety lead-in period without regard for *FGFR* alteration status.

After the first 6 patients have completed one cycle of treatment, a safety analysis will occur. After confirmation of the safety of the combination, a total of 20 additional patients will be enrolled into each of the following 2 cohorts:

- Cohort A: Patients with UC and *FGFR3* mutation or *FGFR1-4* fusion/rearrangement. Patients will be enrolled based on local results, but tissue samples will be archived for retrospective confirmation at a central lab using next-generation sequencing (NGS).
- Cohort B: All other patients with UC (including patients with other *FGFR* or non-*FGFR* genetic aberrations and patients with WT [non-mutated] tumors)

A second safety analysis will occur after enrollment of a total of 10 patients (including the 6 patients from the safety lead-in), in order to confirm the safety profile of the combination before proceeding to the enrollment of the remaining patients in Cohorts A and B.

Please note: At each safety analysis, the combination of futibatinib and pembrolizumab will be considered intolerable if the incidence of unacceptable toxicity including dose-limiting toxicity (as defined in the protocol) is $\geq 33\%$. If the combination is determined to be intolerable, the study may continue with a reduced dose of futibatinib (16 mg QD) if medically appropriate in the opinion of the Investigators and Sponsor.

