3. INVESTIGATIONAL PLAN

3.1. Overview of Study Design

Study TAS-120-203 is an open-label, nonrandomized, multicenter Phase 2 study evaluating the combination of futibatinib and pembrolizumab in patients with advanced or metastatic UC who are not candidates to receive a platinum-based treatment regimen.

The design is briefly summarized in Figure 1.

Abbreviations: FGFR=fibroblast growth factor receptor; I.V.=intravenous; mg=milligrams; PD=progressive disease; PO=oral; QD=daily; Q3W=every 3 weeks; Tx=treatment.

Figure 1: Study Schema

A treatment cycle is defined as 21 days. All enrolled patients will receive the same treatment regimen:

- Futibatinib at an oral (PO) dose of 20 mg daily (QD); and
- Pembrolizumab at an intravenous (I.V.) dose of 200 mg every 3 weeks (Q3W).

Treatment will continue until disease progression, unacceptable toxicity, or any other of the criteria for treatment discontinuation is met; of note, pembrolizumab may be administered for a maximum of 35 doses or a maximum duration of 2 years, whichever is earlier.

The study will begin with a safety lead-in period. During this period, a total of 6 patients with advanced or metastatic urothelial carcinoma will be enrolled and treated for at least one 21-day cycle. Patients will be enrolled into this initial safety lead-in period without regard for *FGFR* alteration status.

After the first 6 patients have completed one cycle of treatment, the first safety analysis will occur. After confirmation of the safety of the combination, a total of 20 additional patients will be enrolled into each of the following 2 cohorts:

- **Cohort A:** Patients with UC and *FGFR3* mutation or *FGFR* fusion/rearrangement. Patients will be enrolled based on local results but tissue samples will be archived for retrospective confirmation at a central lab using next generation sequencing (NGS).
- **Cohort B:** All other patients with UC (including patients with other *FGFR* or non-*FGFR* aberrations and patients with WT [non-mutated] tumors)

A second safety analysis will occur after enrollment of a total of 10 patients (including the 6 patients from the safety lead-in), in order to confirm the safety profile of the combination before proceeding to the enrollment of the remaining patients in Cohorts A and B.

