5.2. Definition of Dose-Limiting Toxicity

For this study, unacceptable toxicity will include any event meeting the criteria for dose-limiting toxicity (DLT), as outlined below. An adverse event not meeting the criteria for a DLT may also be considered an unacceptable toxicity, if it is not tolerable in the long-term and necessitates discontinuation of one or more elements of the combination therapy.

DLT Definition

All toxicities will be graded using the National Cancer Institute – Common Terminology Criteria for Adverse Events (NCI-CTCAE) Version 5.0, based on Investigator assessment. The occurrence of any of the following toxicities during Cycle 1 will be considered a DLT, if assessed by the Investigator to be related to study treatment administration.

- Grade 4 nonhematologic toxicity (not laboratory)
- Grade 4 neutropenia lasting >5 days
- Grade 4 thrombocytopenia of any duration

- Grade 3 thrombocytopenia associated with clinically significant bleeding
- Any nonhematologic AE \geq Grade 3 in severity, with the following exceptions:
 - Grade 3 fatigue lasting \leq 3 days;
 - Grade 3 diarrhea, nausea, or vomiting without use of anti-emetics or anti-diarrheals per standard of care;
 - Grade 3 rash without use of corticosteroids or anti-inflammatory agents per standard of care.
- Any Grade 3 or Grade 4 nonhematologic laboratory value if:
 - Clinically significant medical intervention is required to treat the patient, or
 - The abnormality leads to hospitalization, or
 - The abnormality does not recover to Grade \leq 1 within 48 hours despite best supportive care, or
 - The abnormality results in a drug induced liver injury
 - Exceptions: clinically nonsignificant, treatable, or reversible laboratory abnormalities including liver function tests, uric acid, hyperphosphatemia, etc.
- Febrile neutropenia Grade 3 or Grade 4:
 - Grade 3 is defined as ANC $<1000/\text{mm}^3$ with a single temperature of $>38.3^\circ\text{C}$ (101°F) or a sustained temperature of $\geq38^\circ\text{C}$ (100.4°F) for more than 1 hour
 - Grade 4 is defined as ANC $<1000/\text{mm}^3$ with a single temperature of $>38.3^\circ\text{C}$ (101°F) or a sustained temperature of $\geq38^\circ\text{C}$ (100.4°F) for more than 1 hour, with life-threatening consequences and urgent intervention indicated.
- Grade 3 or higher visual impairment
- Prolonged delay (>2 weeks) in initiating Cycle 2 due to treatment-related toxicity

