5.8. Interim Analyses

The first interim analysis of safety will be performed after the first 6 patients in the safety lead-in period have completed cycle 1 of treatment. The second interim analysis of safety will be performed after a total of 10 patients (including the initial 6 patients enrolled in the safety lead-in period) have completed cycle 1 of treatment.

Additional ad-hoc interim analysis for safety or efficacy may be performed as deemed as appropriate.

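### The second safety look is triggered by 10 patients enrolled in the protocol and SAP 3.1 but by 10 patients completing Cycle 1 in SAP 5.8, so the gate may be run on immature DLT data

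*Protocol*

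**What the plan says.** **First look.** Protocol 3.1 ties it to completed treatment: "After the first 6 patients have completed one cycle of treatment, the first safety analysis will occur". The SAP agrees.

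**Second look, enrolment trigger.** Protocol 3.1: "A second safety analysis will occur after enrollment of a total of 10 patients (including the 6 patients from the safety lead-in". Protocol 11.2: "a second interim analysis of safety will be performed after a total of 10 patients have been enrolled". Both synopsis passages (overall design and interim analyses) and SAP 3.1 also count enrolled patients.

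**Second look, completion trigger.** SAP 5.8 requires that the 10 patients "have completed cycle 1 of treatment". SAP section 8 declares no change to the planned analyses.

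**Purpose.** Protocol 3.1 gives it as "in order to confirm the safety profile of the combination before proceeding to the enrollment of the remaining patients in Cohorts A and B".

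**Rule.** The combination is considered intolerable if the incidence of unacceptable toxicity is at least 33% (synopsis design text, Protocol 3.1, SAP 3.1). The synopsis paragraph on interim analyses says above 33%.

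**What counts.** Under Protocol 5.2, DLTs are related toxicities occurring during Cycle 1, which lasts 21 days. One item is "Prolonged delay (>2 weeks) in initiating Cycle 2 due to treatment-related toxicity". Unacceptable toxicity is wider than DLT. It can include an event that is not tolerable in the long term and forces discontinuation of part of the combination, and that clause is not limited to Cycle 1.

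**Denominator.** None is given for either look. Safety analyses default to the All Treated Population (at least one dose). No DLT-evaluable set appears in the visible text; one population is redacted.

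**The concern.** A look that judges Cycle 1 events needs patients who have been through Cycle 1. The protocol applies that logic to the first look and drops it for the second. A site or safety team working from Protocol 11.2 could run the second look as soon as patient 10 is enrolled, when the newest patients may have only days of follow-up. If those patients are in the denominator, as the All Treated default would have it, they count as event-free and pull the observed incidence down against the 33% rule.

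At stake is the gate to the rest of the trial: about 46 planned minus 10 enrolled leaves about 36 patients.

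**Working it through.** The plan states no operating characteristics for the safety looks, so there is no figure to reproduce.

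**Inputs from the documents:** 6 and 10 patients; the 33% threshold; a 21-day cycle; a delay item of more than 14 days.

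**Assumptions, not in the documents:** a true per-patient event probability *p* of 33%, 40% or 50%, with independent patients; and *m*, the number of the four added patients with Cycle 1 data at the look, from 0 to 4.

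**Step 1: event counts.** 1/6 = 16.7% passes the first look and 2/6 = 33.3% triggers it. At 10 patients, 3/10 = 30% passes and 4/10 = 40% triggers. The two forms of the threshold (at least, or above, 33%) give the same counts. A study that passed the first look on Cycle 1 DLTs therefore carries 0 or 1 event.

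**Step 2: what Cycle 1 DLTs can reach with denominator 10.** The largest count is 1 + *m*.
- *m* = 0: 1/10
- *m* = 1: 2/10
- *m* = 2: 3/10 = 30%, still below the rule
- *m* = 3: 4/10
- *m* = 4: 5/10

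With *m* of 2 or less, Cycle 1 DLTs alone cannot trigger the rule.

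**Step 3: chance of triggering after a passed first look, complete data (*m* = 4).** With 0 events in the first 6, all 4 new patients must have an event. With 1 event, at least 3 of 4 must.

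P(trigger | pass) = [(1−p)^6 · p^4 + 6p(1−p)^5 · (4p^3(1−p) + p^4)] / [(1−p)^6 + 6p(1−p)^5]

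- p = 0.33: (0.09046 × 0.01186 + 0.26732 × 0.10817) / 0.35778 = 8.4%
- p = 0.40: (0.04666 × 0.02560 + 0.18662 × 0.17920) / 0.23328 = 14.8%
- p = 0.50: (0.01563 × 0.06250 + 0.09375 × 0.31250) / 0.10938 = 27.7%

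**Step 4: incomplete data.** The same enumeration with *m* new patients gives:

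| *m* | Denominator 10: p = 33% / 40% / 50% | Denominator 6 + *m*: p = 33% / 40% / 50% |
|---|---|---|
| 0 | 0 / 0 / 0 | 0 / 0 / 0 |
| 1 | 0 / 0 / 0 | 0 / 0 / 0 |
| 2 | 0 / 0 / 0 | 8.1% / 12.8% / 21.4% |
| 3 | 2.7% / 5.1% / 10.7% | 19.9% / 29.4% / 44.6% |
| 4 | 8.4% / 14.8% / 27.7% | 8.4% / 14.8% / 27.7% |

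With denominator 10, missing follow-up always lowers the chance. With an evaluable-only denominator it need not: at *m* = 3 the rule needs 3/9 rather than 4/10, and the chance is higher than with complete data. The operating characteristics thus depend on a denominator that the plan leaves open.

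**Step 5: the Cycle 2 delay item.** It is settled at about day 21 + 14 = 35. Under SAP 5.8 timing, patients 7 to 10 enrol after the first look and then complete 21 days, so every lead-in patient is at least at day 21 + 21 = 42 by the second look. The item can still be open only in patients 7 to 10.

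**The case against.** The best defence is that SAP 5.8 simply supplies the detail. The protocol defers statistical methods and data handling to the SAP (Protocol 11 and 11.4), and a look placed after 10 enrolments sets an earliest time, not an exact one. Staggered enrolment may also mean that some of the four already have data. This is fair as far as it goes, but nothing in the protocol requires waiting, and SAP 3.1 repeats the enrolment trigger.

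Four stronger readings are tempting, and the documents do not support them.

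- A reader might infer that patients without DLT data certainly count in the denominator. No denominator is stated; this is an inference from the All Treated default.
- A reader might infer that the observed rate cannot exceed 1/10, so the rule cannot trigger whatever the true toxicity. That needs denominator 10 and no events seen in any of the four. Patients 7 to 10 can have a DLT before finishing Cycle 1, and the lead-in patients can still accrue non-DLT unacceptable toxicity.
- A reader might blame the timing for the low chance of triggering. Most of it is inherent: after a passed first look, at least 3 of 4 new patients must have events, even with complete data.
- A reader might infer that both looks precede the Cycle 2 delay item for everyone. Step 5 shows that this is too broad.

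The wish for a statement that further enrolment waits for the look is also largely met already by the purpose given in Protocol 3.1, the synopsis and SAP 3.1.

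**Conclusion.** Wrong as written. One safety gate has two incompatible triggers, the SAP carries both, and the one in the protocol allows the look to be run before the newest patients have meaningful DLT follow-up.

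The size of the effect rests on an assumed denominator of 10. On that assumption, Cycle 1 DLTs alone cannot trigger the rule when no more than two of the four added patients have Cycle 1 data. With three, the chance is 2.7% to 10.7% over assumed true rates of 33% to 50%, against 8.4% to 27.7% with complete data. These figures condition on a passed first look and leave out later non-DLT events.

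Aligning the timing removes the dilution. It does not make the second look sensitive: at a true rate equal to the threshold, the look would still miss more than nine times in ten after a passed first look.

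**What to change.** 1. Reconcile both synopsis passages, Protocol 3.1, Protocol 11.2 and SAP 3.1 with SAP 5.8, so that every passage ties the second look to 10 patients with completed Cycle 1 data.
2. State the denominator: DLT-evaluable patients, meaning those who have completed Cycle 1 or have already had an event.
3. Say that the Cycle 2 delay item will be updated for any of patients 7 to 10 in whom it is still open at the look.
4. Report the chance of triggering at each look, so that the limit shown in Step 3 is acknowledged.

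The cost is wording, plus a pause in enrolment of about 3 weeks after patient 10, or up to about 5 weeks if the delay item is awaited.
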